4.2.1.2. Risk Factors

Glycemic Control. Studies among children and youth with diabetes generally report a constellation of related socio-demographic factors that are associated with poor glycemic control, including race/ethnicity, socioeconomic status, lower parental educational attainment, parental involvement in diabetes management, and family dynamics $^{(81-87)}$. Similar patterns were observed in SEARCH, both for T1 and T2D youth $^{(11)}$, and may be partly mediated by our observation of worse glycemic control among T1D youth on insulin regimens other than CSII $^{(24)}$. In SEARCH, 17% of youth with T1D (n=3947) and 27% of T2D (n=552) respectively had poor glycemic control (HbA_{1c}> 9.5%). For both T1 and T2D, higher A1c was also associated with higher concentrations of apoB and LDL particle size $^{(88)}$, and elevated ACR $^{(68)}$, suggesting possible links early in the history of diabetes between glycemic control and future risk for both macro- and microvascular disease that require further study.

Cardiovascular (CV) Risk Profile. CV risk factors track from childhood to adulthood $^{(89, 90)}$ and risk factors measured in youth predict adult target organ damage $^{(91-93)}$. Thus, an adverse risk profile among youth with diabetes may magnify the already three-fold excess risk for CV mortality associated with diabetes in adulthood $^{(94)}$. In SEARCH, we found that T1 youth had a prevalence of overweight (22%) that was significantly higher than that of non-diabetic counterparts, and ~ 90% of youth with T2D were overweight or obese $^{(95)}$. The prevalence of metabolic syndrome among SEARCH youth with T1D was 14%, and 92% for youth with T2D $^{(96)}$. Further, among youth with T1D, 11% had elevated apoB, 8% had dense LDL, and 12% had elevated LDL-cholesterol. In contrast, among youth with T2D, 36% had elevated apoB, 36% had dense LDL, but only 23% had elevated LDL-cholesterol. Moreover, the prevalence of elevated blood pressure in youth with type 1 was 5.9%; minority ethnic groups, obese adolescents and youth with poor glycemic control were disproportionately affected. In contrast, 23.7% of adolescents with type 2 diabetes had elevated BP (p<0.0001) $^{(97)}$.

Psychosocial factors. Psychosocial factors are important to consider in the adaptation to and treatment of childhood diabetes $^{(98-100)}$. Family conflict and communication have also been associated with HRQoL in youth with T1D $^{(101)}$ and with poorer metabolic control $^{(102)}$. In addition, a higher level of parental fear of hypoglycemia was associated with poorer glycemic control in their child $^{(103)}$. From SEARCH, youth from racial and ethnic minority groups had a higher rate of depressed mood than did NHWs $^{(104)}$. Depressed mood was associated with higher HbA_{1c} $^{(104)}$ and among youth with T1D, poor glycemic control was associated with lower generic $^{(105)}$ and diabetes-related health-related quality of life (HRQoL) $^{(106)}$. The SEARCH Cohort Study will provide urgently needed longitudinal studies in large and diverse cohort regarding the impact of psychosocial factors on the health of youth with diabetes.

Behavioral factors. Helgeson et al ⁽¹⁰⁷⁾ reported high dietary fat intake among youth with T1DM. Regarding physical activity, a majority of youth with T1D from a Norwegian cohort did not meet physical activity recommendations ⁽¹⁰⁸⁾, and lower

physical activity was associated with higher A1c and worse lipid profile ⁽¹⁰⁹⁾. From SEARCH, dietary intake of adolescents with T1DM is high in total and saturated fat, and low in fiber, fruits and vegetables compared to current nutrition recommendations ⁽¹¹⁰⁾, with similar patterns among those with T2D. In youth with T1D, a higher adherence to DASH diet was inversely related to hypertension ⁽¹¹¹⁾. Also, substantial proportions of youth with either T1 or T2D across race/ethnic groups engaged in less physical activity than recommended ⁽⁶⁻⁸⁾. Of major concern, prevalence of current smoking ranged from 12-20% for T1D adolescents, and from 13-26% among T2D adolescents across race/ethnic groups ⁽⁶⁻⁹⁾.

Summary. The SEARCH Cohort Study will provide comprehensive information on the prevalence and incidence of key metabolic, psychosocial, and behavioral risk factors, and their association with acute and chronic complications of diabetes, and diabetes-related quality of life. These phenomena will be evaluated in a socio-cultural context, particularly considering race and ethnicity.

4.2.1.3. Effect of Barriers, Care Quality, and Transition to Adult Care on Outcomes

Timely receipt of high quality health care is important for children with special health care needs (CSHCN), ⁽¹¹²⁻¹¹⁵⁾ including diabetes. However, a chasm exists between ideal and actual care ⁽¹¹⁶⁻¹¹⁸⁾ among those of minority race/ethnicity and low socioeconomic status who continue to face barriers to quality health care ⁽¹¹⁹⁻¹²²⁾ and health disparities, ⁽¹²³⁾ including diabetes-related mortality ⁽¹²⁴⁾.

Data from SEARCH demonstrate that a substantial proportion of parents report barriers to care including cost of care (41.2%) and medication (25.2%), not receiving family-centered care (31.3%), and problems communicating with doctors (43.3%) ⁽¹²⁵⁾. Being from a racial or ethnic minority group and having a lower income were associated with less access to care and reduced adherence to ADA guidelines for care. Further study is needed to elucidate the relationship of quality of care to outcomes, and specific barriers to care experienced by participant groups who most often do not receive recommended care.

To address this issue, we adapted a conceptual model describing children's interactions with the health care system and how barriers to high quality care reduce the likelihood of improved health outcomes of importance to diabetes ⁽¹²⁶⁾, and incorporated this model into the overall conceptual framework of the SEARCH Cohort Study (see Figure 3, Section 4B.) Barriers to care interact in very complex ways with biological and social factors, sometimes as confounders, other times they act as mediators, and occasionally they can modify the associations of interest. Commonly, clusters exist of biological, social and system-related risks. Our model hypothesizes a direct effect of biological risk factors on outcomes, and further proposes that barriers to care, quality of care, transition of care, and behavioral risk

Section 4B - Study Objectives/Background and Significance (Phase 3 - 12/2010) Section 4B - Page 11 Cohort Study

factors can affect biological factors over time, thereby altering outcomes. Finally, the model hypothesizes a link between socio-cultural factors (e.g. race/ethnicity) and both biological risk factors (e.g. dimensions of diabetes type) and mediators (e.g. barriers to care).

Transition of care from pediatric to adult health care is a dynamic process that seeks to meet the health care needs of each person as he or she moves from childhood to adulthood ⁽¹⁾. In contrast, 'transfer of care' denotes the single event of changing from a pediatric to an adult provider. Very little epidemiological research has been published that had examined the processes or outcomes associated with transition or transfer of care. Several publications describe transition of care focusing on specific programs for individuals with a chronic disease ⁽¹¹³⁻¹¹⁸⁾. These studies are qualitative. They describe the average age of transfer of care as 18 years (range 13-25 yrs) ^(121, 126 - 127), deterioration in obtaining clinical care with a decrease in the frequency of health care visits and an increase in hospitalization rates (11, 28, 128), variation in glycemic control^(8, 120), and no change in the frequency of adverse outcomes including hypoglycemia or diabetic ketoacidosis ^(128, 129). This literature suggests that programs utilizing transition clinics had the greatest success ^(122, 123, 130). Importantly, all of these studies describe experience of transition outside the US where health care systems are quite different (119-134). In the United States, concerns about losing health insurance and the potential effect of under-insurance on young adults with chronic health conditions has been a major consideration in research on transition to adult care ⁽¹³⁰⁾. However, with the passage of comprehensive health reform in March 2010, young adults may continue on their parents' insurance until the age of 26 years if they do not have jobs that offer health insurance and if they can still be claimed as dependents on their parents' taxes, regardless of whether they are students or are employed. An opportunity exists to study how this new national policy may affect transition of care for young adults with diabetes by comparing SEARCH participants who transferred care before, versus after, health care reform is initiated.

Specifically from SEARCH, for individuals age 17 or older participating in the SEARCH 2001 prevalent cohort Quality of Care Survey, 66% of those with T1D reported seeing an adult provider as the main source of diabetes care, and 57% reported having discussed the transition to adult care with their health care provider. For T2D, 85% were seeing an adult provider, and 49% reported having discussed their transition of care. The median age of transition of care was 18 yr for T1D, and 19 yr for T2D.

Given the crucial role that high-quality care plays in health outcomes, understanding the effect of barriers to care and health-care quality on diabetes outcomes over time is critically important. Determining which barriers or aspects of quality affect outcomes for which groups of individuals, how these processes interact with transition from pediatric to adult diabetes care, and whether and how new health insurance rules affect the transition process, would enable researchers to develop interventions to improve outcomes for youth with diabetes. Study of transfer of care before and after health care reform highlights a major strength of this proposal - the ability to test new research questions seamlessly within the existing structure SEARCH.

4.2.1.4. Summary of Significance of the SEARCH Cohort Study to the Field of Childhood Diabetes

Across a wide range of topics including biological, behavioral, and socio-cultural characteristics, processes of health care and quality of care, the SEARCH study has already substantially contributed to our understanding of the impact of diabetes in youth. The SEARCH Cohort Study will add estimation of complications in the modern era of treatment, and allow exploration of a wide variety of interacting biological, socio-cultural and health care factors that may alter the risk of such complications. Our findings will significantly inform clinical and public health practice and policy, as well as provide direction to new research, all targeted to reduce the impact of diabetes on the health and well-being of youth with diabetes.

Reference List

- 2. Incidence and trends of childhood Type 1 diabetes worldwide 1990-1999. *Diabet Med* 2006 Aug;23(8):857-66.

5.1 AIM 1: TEMPORAL TRENDS

5.1.1. Overview of Design, Methods and Data Collection

Centers in SEARCH Phase 3 will continue to conduct population-based ascertainment of cases of diabetes in youth less than 20 years of age in the year of diagnosis for the period 2010 - 2014, using methods consistent with those employed in SEARCH Phase 1 and SEARCH Phase 2. This will involve identification, validation, confirmation of eligibility and uniqueness of cases, and registration of the case both locally with identifiers and centrally with the SEARCH 3 Coordinating Center (CoC) without identifiers. The 2010 - 2014 cases will have their medical records abstracted and will be asked to complete a brief survey. A sample of 2012 cases will be invited to an in-person research visit. Case registration will proceed without disruption in the transition from the end of SEARCH Phase 2 (September 29, 2010) until the full implementation of the SEARCH Phase 3 protocol. All data collection will be performed under standardized protocols by centrally trained and certified staff.

5.1.2. Case Ascertainment Processes

Ongoing Case Ascertainment: The case ascertainment, validation, eligibility, and deduplication protocol in SEARCH 3 will be the same as the one used in SEARCH 1 and 2 to ensure continuity and comparability across time and centers. SEARCH 3 will continue to use the reporting network of clinics and health care providers that was established previously as the primary approach to case-finding for incident cases of diabetes for the period 2010-2014. The case ascertainment approach involves existing validated pediatric diabetes databases, hospital and health plan databases, and other health care organizations. Center-specific case ascertainment methods are presented in Section 2.

Case Validation: Cases of diabetes will be validated based on provider reports, medical record reviews, or self-report of a physician diagnosis of (non-gestational) diabetes. A physician-diagnosed case of diabetes is established if any of the following criteria are met: (1) medical record review indicating a physician diagnosis of diabetes, (2) the diagnosis of diabetes is directly verified by a physician, (3) the physician referred a youth with diabetes to the study, or (4) the case was included in a clinical database that had a requirement for verification of diagnosis of diabetes by a physician.

Eligibility Criteria: Eligibility criteria will remain the same. As in SEARCH 1 and 2, the study will be confined to children/youth who, in addition to having an onset of physician-diagnosed of diabetes in the index year, are also are < 20 years of age on December 31 of the index year and 2) are resident of the population defined for geographically-based centers at any time during the index year, or a member of the
participating health plan for membership-based centers at diagnosis, and 3) are not active duty military personnel or institutionalized. Protected Health Information (PHI) will be obtained in order to validate and confirm eligibility and uniqueness of cases in keeping with HIPAA and the procedures and approvals required by the local IRB.

De-duplication: Duplicates will be identified using both electronic files and manually, both within and between case sources, using the name or initials, gender, date of birth, ethnicity, zip code, or other available information, in keeping with HIPAA requirements to use the least amount of PHI in conducting research. The number of duplicates identified will be used to estimate completeness of ascertainment with the capture-recapture method among the geographic centers.

Systematic re-ascertainment: A systematic case re-ascertainment process will be conducted in 2012 for cases incident in 2006-2010 and in 2014 for 2008-2012 cohorts. The purpose of re-ascertainment is to assure as complete ascertainment of diabetes cases as possible, especially those with T2D, who, due to different care patterns, we theorize are more likely to be missed by the SEARCH network prior to the close of the registration window. Additional cases will be registered with the center and the CoC with a flag to indicate that they were registered outside of the standard window.

Case Registration: Cases that are valid, eligible and unique will be registered by the center with information being uploaded to the CoC. Minimal information about the participant (age, gender, race/ethnicity, type of diabetes reported by clinician, center, date of diagnosis, zip code or county of residence, and birth date) will be uploaded to the CoC website in order to protect confidentiality. Names and addresses are not provided to the CoC. In cases where duplicates and cases that are not valid or eligible are identified at a later date, they will be unregistered by both the local center and the CoC.

Collection of Core Variables: A minimum amount of demographic and clinical information is needed for all registered cases in order for the study to be able to provide population-based rates of diabetes mellitus by age, gender, diabetes type and race/ethnicity for the entire population of cases. This information is also critical in assessing possible response bias to the in person research visit. This information is called "core" information. The main sources of core data are medical records and the initial participant survey and are described in Table 5 - 1.

Medical Record Abstraction (MRA) serves the following purposes: a) validation of diabetes diagnosis; b) main source of core demographic and diagnostic information, and c) secondary data source for race/ethnicity information. In SEARCH 2, an additional set of items pertinent to clinical presentation was added to the medical record abstraction effort: weight/height at diagnosis, DKA at diagnosis and insulin use history. We will continue to collect these data through MRA in SEARCH 3 and will seek 100% completion.

Initial Participant Survey (IPS) contains key data, including the core information described above, and serves to: a) verify of case eligibility (e.g., residence in the year of diagnosis); and b) is the main source for self-reported race/ethnicity information. Additional information includes: symptoms at presentation, potential secondary causes of the diabetes, use of insulin and other medications, treatment history, family structure, usual language spoken, and contact information (for local use only). The IPS can be self-administered or interviewer-administered. The information can be collected online, by phone or in person, or at the beginning of the in-person research visit. To encourage participation in the IPS, a monetary incentive of \$10.00 will be offered. We will continue to collect these data through IPS in SEARCH 3 (Table 5 - 1) and will seek 90% completion.

In-Person Research Visit (IPV): The IPV or "registry visit" in SEARCH 3 is designed to collect data on relevant dimensions of diabetes type (presence of autoimmunity, genetic susceptibility to autoimmunity, insulin sensitivity, insulin secretion) and data informing the clinical presentation of diabetes. We will also store (by separate consent) blood, serum, plasma and urine for future genetic and non-genetic analyses. In keeping with the time-stratified sampling approach initiated in SEARCH 2, only the incident 2012 cohort will be eligible to participate in the registry visit. An additional sampling approach will be implemented in SEARCH 3, in order to reduce participant burden and maximize study resources, without compromising the statistical power to detect trends in clinical characteristics over time. To maximize the number of minority participants and youth with T2D, eligible cases for SEARCH 3 registry visit are all cases >10 years old, regardless of ethnicity/race, all minority cases, regardless of age, all cases not T1, regardless of race or age, and 50% of NHW T1 cases <10 years old. Since some sites are not able to obtain race at the time of the assignment of the PID, if race is not available, all participants will be invited to the IPV. We will seek a 70% completion of the IPV among eligible youth.

Table 5-1: Summary of SEARCH3 Registry Data Collection						
	Eligible Cohorts	Core Variables	Clinical Presentation			
MRA	2010-2014	Date of birth, date of diagnosis, sex, provider- determined diabetes type, race/ethnicity, residence in the year of diagnosis	Weight/height at diagnosis, DKA at diagnosis, insulin use, acanthosis nigricans, diabetes autoantibodies and c-peptide assessment			
IPS	2010-2014	Date of birth, date of diagnosis, sex, self-reported race/ethnicity, residence in the year of diagnosis; health insurance; usual diabetes care, education of parents; youth > 18 yrs.	Treatment history, secondary diabetes, symptoms at presentation, acute complications, medications, family history, contact information; reported height, weight			
IPV	2012		 Physical Exam: height, weight, waist circumference, BP, acanthosis nigricans Medication Inventory: list of currently prescribed medications Lab/specimens: diabetes autoantibodies (GAD65, IA2), HbA_{1c}, fasting glucose, C-peptide, lipids, urinary albumin/creatinine (spot sample) Repository: serum, plasma, DNA (by separate consent) and urine for storage on 1st morning void 			

The content of the IPV for incident cases will be similar to SEARCH 1 and 2 (Table 5 - 1). However, unique to SEARCH 3, we will add a first morning void urine collection that the participant will bring to the clinic. Urinary albumin and creatinine will be measured to obtain an albumin/creatinine ratio on a spot urine sample. Samples will not be collected during the visit on participants who are pregnant or menstruating, have had a fever greater than 100 degrees in the past two hours, or who have taken an antibiotic in the past seven days for a urinary tract infection. A dipstick test will also be performed to test for the presence of blood or leukocytes by the central laboratory. Urine will also be stored (first morning void only) to assess other markers of nephropathy in the future. (8/11)

The following will be collected for the IPV incident cases: fasting blood and urine for laboratory measurements and storage, and a brief physical examination as outlined below.

• Blood measures: Diabetes autoantibodies (GAD65, IA-2); (ZNT8 will be added after the assay is standardized); HbA_{1c}, fasting glucose and C-peptide, lipids (total

cholesterol, HDL-Cholesterol, LDL-Cholesterol, triglycerides), HLA risk genotypes

- Urine measures (spot and first morning void): Urinary albumin and creatinine (from spot urine collection)
- Physical examination: Height, weight, blood pressure, assessment of acanthosis nigricans, waist circumference (NHANES and minimum waist methods) on participants who are 3 years of age or older at the time of the visit
- Medication inventory: List of currently prescribed medications.

SEARCH participants with an IPS will be invited to complete the IPV if they meet the following eligibility criteria. If <10 years of age and have type 1 diabetes, we will invite 50% of non-Hispanic White and 100% of all minority youth to participate in the IPV. All youth with type 2 diabetes will be invited to the visit. To encourage IPV participation, a remuneration of \$80.00 in cash or gift cards will be offered. Some centers may offer assistance with transportation in order to facilitate these visits. We will seek to complete a 70% rate among those participants invited to the IPV (Table 5-2).

Table 5-2. Estimated Number of Cases Registered, and Participating in the IPS and IPV								
Per Year								
Center	Estimated 2	N Incide	nt cases/year	Estimated N	Estimated N			
	NHW<10	Other	Total	IPS/year	IPV/year*			
SC	70	206	276	248	179			
OH	51	113	164	147	104			
СО	132	244	376	338	236			
CA	15	213	228	205	156			
WA	75	154	229	206	145			
Total	343	930	1,273	1,144	820			

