	2001 Prevalent	2002 - 2005 Incident	2006 - 2009 Incident	2009 Prevalent	2010 Incident
Case Registration	Х	Х	Х	Х	Х
Initial Participant Survey (IPS)	Х	Х	X	x (for cases not incident in other years)	Х
In-Person Visit (IPS)	Х	Х			x (through September 2010)
Typology Visit			x (2006 and 2008 only)		

Extended Typology	Х	Х			
12, 24, 60 Month Follow-Up		Х			
Annual follow-up for contact information	х	х	х	Х	х

SEARCH Phase 3 Objectives

Five of the original six SEARCH 1 and 2 centers were funded to participate in SEARCH3: (Carolinas, Ohio, Colorado, California, and Washington). The objectives of SEARCH Phase 3 include a registry component and a cohort component. Each component will be performed at all five clinical centers. In SEARCH Phase 3, many of the measurements which were collected during SEARCH Phases 1 and 2 will continue to be collected; additionally, there will be unique measurements collected for each component of SEARCH Phase 3.

Registry Study

The SEARCH for Diabetes in Youth Registry Study will continue to ascertain newly diagnosed incident diabetes cases in youth age < 20 years across five geographically dispersed Study Centers in order to accomplish the Specific Aims shown below. The study will continue to identify incident cases from September 30, 2010 through September 29, 2015, and will periodically re-ascertain cases from earlier years.

Aim 1: To continue to ascertain newly diagnosed (2010 - 2014) incident diabetes cases in youth age < 20 years in order to assess temporal trends in diabetes incidence and temporal trends in presentation of diabetes for the period 2002-2014, by age, sex, race/ethnicity, and diabetes type.

Specific characteristics to be examined are: age at onset of diabetes, markers of disease severity (diabetic ketoacidosis, residual insulin secretion, HbA_{1c}), immunogenetic markers (diabetes autoantibodies, HLA risk genotypes), markers of insulin sensitivity (insulin sensitivity score, waist circumference, body mass index), cardiovascular risk factors (lipid profile, blood pressure, microalbuminuria).

Aim 2: To provide consultation and support to inform the development of low-cost sustainable public health surveillance systems of childhood diabetes in the U.S., with a focus on challenges in ascertainment of cases with T2D and cases among older youth (ages 15 years or older) with any form of non-gestational diabetes.

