centralized source for validation of case status (such as pathology laboratory reports for cancer). In the U.S., increasing concerns about privacy and confidentiality have led individual hospitals or providers to refuse to participate in registries. It is critical in the estimation of incidence rates and temporal tends in rates that case ascertainment be virtually complete, and if incomplete, that the degree of ascertainment be consistent over time. The relatively low frequency of diabetes occurrence requires longer time periods and larger populations for stable rate and trend estimates. There is also reluctance on the part of older youth and young adults to participate in registration activities. Many of the limitations in developing registries of diabetes in youth in the U.S. are inherent in the underlying health care system (lack of common health identification system, multiple and fragmented care sites, privacy concerns, data systems designed to address only billing) and are not due to the registries themselves. As demonstrated by the SEARCH for Diabetes in Youth registry, the majority of such limitations can be successfully addressed, resulting in unbiased estimates of rates and disease-risk factor associations.

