6.1. TEMPORAL TRENDS IN INCIDENCE OF DIABETES (Research Questions 1.1 & 1.2)

SEARCH has ascertained each new case of T1D and T2D in its surveillance areas since 2002, allowing us to estimate the incidence of diabetes over time. We will continue this surveillance in SEARCH 3, and a primary objective is to assess the significance of changes in the incidence of T1D and T2D over time, overall and by levels of important characteristics such as age, sex, and race/ethnicity, and to determine if the changes over time vary by these characteristics.

Chi-square tests will be used to determine if the incidence of diabetes changes over time, overall and by characteristics of interest. The chi-square test is robust against a large range of possible differences; however, it is not particularly powerful for detecting specific patterns. While numerous patterns of change are possible (consistently increasing, consistently decreasing, increasing then decreasing, decreasing then increasing, etc.), we are primarily interested in detecting consistently increasing or decreasing changes over time. The Cochran-Armitage trend test will be used to determine if the changes over time are increasing or decreasing. In a more general framework, weighted linear regression and logistic regression will be used to assess changes in diabetes incidence over time. These models allow us to assess the effects of characteristics of interest and to determine if the trends differ by levels of the characteristics (e.g., younger vs. older age-groups, NHW vs. minority, males vs. females).

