6.4. EVALUATING CASE ASCERTAINMENT STRATEGIES: ANALYSIS OF SEARCH REGISTRY DATA

For research question 2.1, we will evaluate (a) whether a longer period of calendar time is required to ascertain cases of youth with T2D or older youth with any type of diabetes than youth with T1D and younger youth; (b) whether any calendar time difference in ascertainment by diabetes type and age can be accounted for by the time from clinical diagnosis to hospitalization or receipt of specialty care services; and (c) if there are temporal changes in observed differences in time to case ascertainment. Date of diagnosis, date of birth, sex, clinical diabetes type, type of health care provider (pediatric endocrinologists, pediatricians, family practice physicians, adult endocrinologists) and the system in which each youth with diabetes received their care (community clinic, university based health system, managed health care organization) around the time of diagnosis are obtained from the medical record, the IPS, or administrative data sources at the time of case validation. Calendar time from date of diagnosis to date of case registration will be calculated in months so that time from diagnosis to registration can be compared by type within each category as well as within type by age category.

Using this information from SEARCH registered cases we will be able to quantify the timing and completeness of case ascertainment under a variety of scenarios. For example, we can simulate specific ascertainment scenarios to compare the completeness of ascertainment of youth with T1D versus T2D by age category if a system relied solely on pediatric endocrinology and hospital-based surveillance networks as compared to if a system that relied on these sources plus primary care providers. We will identify efficient ways to optimize ascertainment of youth with T1D or T2D, using data collected to date by the SEARCH study and through the 2011 incident cohort. This approach goes beyond examining variation by study centers and takes advantage of the diversity within and between the existing SEARCH study centers which conduct ascertainment state-wide (SC, CO), in defined regions (WA, OH), from enrollees in managed health care organizations (CA), and from enrollees in IHS facilities.

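### Late re-ascertainment covers incident years 2006-2012 only, and Sections 6.1 and 6.4 do not say how the flagged late cases enter the incidence trend or the time-to-ascertainment comparison

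*Protocol*

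**What the plan says.** Protocol Section 5.1.2 sets two late rounds: "A systematic case re-ascertainment process will be conducted in 2012 for cases incident in 2006-2010 and in 2014 for 2008-2012 cohorts". Its stated purpose is the fullest possible ascertainment, above all of type 2 cases. It adds: "Additional cases will be registered with the center and the CoC with a flag to indicate that they were registered outside of the standard window". The Registry Study text in Section 1 says only that the study "will periodically re-ascertain cases from earlier years", without naming years. It also gives the identification period: "The study will continue to identify incident cases from September 30, 2010 through September 29, 2015".

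Section 4.2.1.1 calls it critical for rates and trends that ascertainment be virtually complete and, "if incomplete, that the degree of ascertainment be consistent over time".

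Section 6.1 plans the 2002-2014 trend analysis: "Chi-square tests will be used to determine if the incidence of diabetes changes over time", followed by the Cochran-Armitage test and regression. For Research Question 2.1, Section 6.4 says: "Calendar time from date of diagnosis to date of case registration will be calculated in months", and asks whether differences in this delay change over time. Neither section mentions the flag.

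**The concern.** Case-finding effort is built to differ by incident year, with the extra effort in the middle of the series. If flagged cases are pooled with the rest, part of any difference between years reflects how often a cohort was searched. The added yield is expected to be mainly type 2, so the distortion would differ by diabetes type, and type-specific trends are Research Questions 1.1 and 1.2.

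The delay analysis is affected more directly. A delay can be measured only for a registered case. A cohort searched again years later can show delays of several years. A cohort never searched again cannot, and the most recent cohorts are also cut off by the end of identification.

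**Working it through.** **1. Late passes by incident year (Section 5.1.2).** 2002-2005: 0. 2006-2007: 1. 2008-2010: 2. 2011-2012: 1. 2013-2014: 0.

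**2. The plan's own detectable slopes (Section 6.1).** Inputs: 24.3 per 100,000 per year overall and 15,000 type 1 and 3,700 type 2 diagnoses a year (Section 4.2.2.1); 5,000,000 youth and 13 years (Section 6.1). Assumed: half the youth are aged 10 or older and all type 2 cases fall there; 80% power at 5% two-sided, as stated for Table 6.1.

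- Type 1 rate: 24.3 × 15,000/18,700 = 19.5 per 100,000.
- Type 2 rate at age 10+: 2 × 24.3 × 3,700/18,700 = 9.6 per 100,000, or about 240 cases a year in 2,500,000.
- Detectable slope = (1.96 + 0.84) × √(rate × 100,000/N ÷ 182), where 182 is the sum of squared deviations of 13 yearly points.
- Type 1: 0.130 (0.67%). Type 2: 0.129 (1.34%). The protocol states 0.13 (0.7%) and 0.13 (1.35%), so both reproduce.

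**3. Effect on type 2 incidence if flagged cases are counted.** True incidence is held flat at 240 cases a year. Completeness in a year with k passes = 1 − (1 − c)(1 − r)^k, where c is in-window completeness and r is recovery per pass. The documents give neither, so c = 80-85% and r = 25-50% are assumptions. The slope is a count-weighted regression of the log expected count on year. The chi-square non-centrality is Σ(count − mean)²/mean on 12 df.

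Example, c = 85%, r = 50%: expected counts are 204 (six years), 222 (four) and 231 (three), with mean 215.8. Non-centrality = (6 × 11.8² + 4 × 6.2² + 3 × 15.2²)/215.8 ≈ 7.8, so a flat series is rejected 39% of the time.

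| c | r | Slope 2002-2014, %/yr | Trend test false positive | Chi-square false positive | Slope 2002-2012, %/yr (false positive) | Slope 2006-2014, %/yr (false positive) |
|---|---|---|---|---|---|---|
| 85% | 25% | +0.22 | 7% | 13% | +0.72 (19%) | −0.65 (11%) |
| 80% | 25% | +0.31 | 9% | 23% | +1.01 (32%) | −0.90 (17%) |
| 85% | 50% | +0.40 | 12% | 39% | +1.29 (50%) | −1.15 (26%) |
| 80% | 50% | +0.57 | 19% | 70% | +1.79 (76%) | −1.57 (42%) |

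The full-period slope is small because the re-ascertained block, centred on 2009, lies close to the middle of the series, 2008.

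**4. Sensitivity.** If 2014 is a further ten points incomplete, the full-period slope becomes −0.13 to +0.23% per year and chi-square rejection rises to 33-88%. If 2002-2005 had one late pass in earlier phases, the slope becomes about −0.2 to −0.6% per year and chi-square rejection falls to 9-37%.

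**5. Type 1.** The 93% completeness in Section 4.2.2.1 is for all types at the four geographic sites. With type 2 at 80-85% and 3,700/18,700 = 19.8% of cases, type 1 completeness is (0.93 − 0.198 × 0.80 to 0.85)/0.802 = 95-96%. At 50% recovery and an assumed 930 type 1 cases a year, chi-square rejection is 11-16%.

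**6. Months from diagnosis to registration.** Assumed: an in-window mean of 6 months, late cases adding 5%, found in mid-2012 (mid-2014 for incident year 2011). Mean = (6 + 0.05 × lag)/1.05.

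- 2002-2005, no late pass: 6.0 months.
- 2006, lag 72 months: 9.6/1.05 = 9.1.
- 2010, lag 24 months: 7.2/1.05 = 6.9.
- 2011, lag 36 months: 7.8/1.05 = 7.4.

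These differences come from the schedule alone. At the other end, a case diagnosed at the close of 2014 has about nine months before identification ends.

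**The case against.** A reader might infer that Section 6.1 commits the study to counting every late case, and that a mid-period rise and fall will be reported as a change in incidence. The text does not go that far. Section 6.1 names tests but defines no case set, and the flag lets an in-window series be separated. The choice may also be made in an analysis plan that is not shown. On the other side, the stated aim of complete ascertainment, and the reference in Section 5.1.2 to rates for the whole population of cases, make counting the flagged cases the more natural reading.

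Other points stand in part:

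- Re-ascertainment serves the first half of the Section 4.2.1.1 condition, near-complete ascertainment. Constancy is the fallback. But completeness is improved for some years only.
- Section 5.1.2 plans capture-recapture, and Section 3.2.1.7 gives one committee oversight of both re-ascertainment and trends. Capture-recapture covers the geographic centers only, and nothing carries it into the trend model.
- Section 6.1 is mainly interested in steady increases or decreases, where the bias is smallest. The chi-square test is nevertheless listed first.
- Late case-finding for 2002-2005 in earlier phases is not described, so even the sign of the slope bias is uncertain.
- Section 6.4 uses data through the 2011 incident cohort for its work on optimising ascertainment. If that limit also covers the delay analysis, the cut-off of 2013-2014 does not arise. The contrast between 2002-2005 and 2006-2011 remains. The standard window's length is not given, so nine months is not shown to be too short.

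**Conclusion.** The point holds in a conditional form. The schedule is uneven across the trend period and, if flagged cases are counted, it conflicts with the protocol's own consistency condition. Sections 6.1 and 6.4 do not prevent this.

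For the 13-year type 2 slope the effect is modest, at most about 42% of the detectable slope (0.57/1.35) under the assumptions used. It does not support a claim that the main linear trend would be created by the schedule. The test for any change and sub-period trends are more exposed. For 2002-2012, the spurious type 2 slope can reach or exceed 1.35% per year at the less favourable assumptions. All these sizes depend on completeness and recovery figures that the documents do not give.

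The firmest part concerns Research Question 2.1. Raw diagnosis-to-registration months compared across cohorts, as Section 6.4 describes, will differ because of the schedule whenever the late passes find cases.

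**What to change.** In Section 6.1, state that the primary 2002-2014 trend counts only cases registered within the same standard window after each incident year, and give the length of that window. Omit 2014 if its window is not complete by September 29, 2015. Report flag-inclusive rates as a secondary analysis, and say what late case-finding 2002-2005 received.

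In Section 6.4, apply the same maximum delay to every cohort, or use a right-truncation (reverse-time) model.

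The cost is wording, since the flag and registration dates already exist. Primary counts and rates for 2006-2012 will be slightly lower. The stated detectable slopes are essentially unchanged, because they assume constant yearly counts at the initial rates. With flagged cases excluded, the late passes no longer add to the trend.
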